4.7. Data Collection

The data collected will not be used for clinical diagnosis or treatment purposes. The data collected will be kept on a password-secured UTMB computer. An encrypted USB flash drive will be used to transfer data. The data will be linked to the patient by the patient's MRN number. This identifier is needed to access and analyze demographic data. During analysis of the data, all identifiers will be deleted. Data will be collected from the patient's chart and the chart of the neonate. The data collected will include demographics and data needed to assess the primary and secondary outcomes listed below. The data collection sheet is uploaded for review by the IRB. It is imperative that studies involving induction of labor and intrapartum care assess the outcomes of the neonate.

6 V4.1 Protocol Version Date: 02/28/2023

Study Summary Flow Diagram

4.8. Primary Outcomes

• Time to vaginal delivery measured from time of initial foley balloon placement to delivery

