University of Texas Medical Branch at Galveston

Research Protocol IRB #21-0327

Title: (Free Foley Trial) Tension versus Tension-Free Foley Balloon for Cervical Ripening in Nullipa-

rous Women Undergoing Induction of Labor: A Cluster Randomized Controlled Trial

Principal Investigator: [name], DO Faculty supervisor: [name]

Funding: Departmental

1. Introduction and Purpose:

Foley balloons are commonly used as a mechanical method of cervical ripening for induction of labor. Foley balloons may be placed either under tension or without tension (tension-free). Currently at UTMB, it is left to the provider to decide which technique is utilized. The purpose of our study is to examine time to delivery in nulliparous women undergoing induction of labor who have a Foley balloon placed as a mechanical cervical dilator, assigned to either tension or without tension. The goal is to determine if there is a potential added benefit to placing the Foley balloon on tension as compared to no tension, both are considered standard of care at our institution. Our hypothesis is that Foley balloon under tension for cervical ripening results in shorter time to vaginal delivery compared to Foley balloon placed without tension.

2. Background:

The rate of induction of labor has increased significantly in the United States. The US National Vital Statistics Report birth data for 2018 reported an induction of labor rate of 27.1% compared to 23% in 2013. 14,15 The rate of induction of labor will likely continue to increase as studies are published demonstrating maternal and neonatal benefits associated with elective 39-week induction of labor. 10 The rate of induction of labor is likely to also continue to increase as the incidence in medical comorbidities continue to increase in the United States. Even though induction of labor occurs in greater than a quarter of births in the United States, significant variation in clinical practice exists in the management of induction of labor. There is significant need to research methods for induction of labor given these shifts in clinical practice and the lack of an accepted standard of care.

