
4.4. Additional Baseline Procedures

- Routine intrapartum care will be provided by the patient's managing obstetric team.
- Trained and experienced study team will be responsible for all research data abstraction.
- The PI and faculty sponsor will review and validate the diagnosis for all subjects identified to have the primary outcomes. If there is uncertainty, a faculty sponsor will review the chart, discuss with the study team as needed, and make a final determination regarding the outcome.

- Maternal outcomes will be assessed following delivery.
- Data collection forms will be used during these processes and charts will be reviewed up to 30 days postpartum. We will collect demographic data, as well as data related to the patient's intrapartum course, delivery, and immediate postpartum period while inpatient.
- Subjects' participation will end following delivery.

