Sample size was calculated based on the determination of superiority. The primary outcome is time in minutes from Foley balloon placement to delivery. For the sample size calculation, based on our prior published data¹⁰, the primary outcome in control arm would be 1053.4 ± 535.73 mins. Using difference rate of 25% (No tension group: 1316.748 mins), power of 80% and 2-sided alpha of 0.05, and the assumption that 10 eligible subjects are induced per week, we previously estimate that we will need 13 clusters (10/cluster) with complete ascertainment. Currently, we have recruited approximately 15 subjects per cluster. For the previously planned 13 clusters in each group (26 clusters total), we estimate a final total number of 405 subjects. Final sample size: 405 (minimum of 130/group). This difference between both methods is clinically significant. Detailed: Estimated sample sizes for a two-sample means test (z test); Study parameters: alpha Since this is a single center study in one same location the intra-cluster correlation coefficient of variance (rho) should be close to 0 and would give us a sample size of 140, but we chose the worst-case scenario of a rho of 0.1 (graph).

This trial will be registered with Clinical Trials Register (Clinicaltrials.gov), before recruitment is initiated and after IRB approval.

SAMPLE SIZE COMPUTATION power twomeans 1053.399 1316.74, sd(535.73) m1(10) m2(10) rho(0.1)

Performing iteration ...

Estimated numbers of clusters for a two-sample means test Cluster randomized design, z test assuming sd1 = sd2 = sd Ho: m2 = m1 versus Ha: m2 != m1

Study parameters:

Cluster design:

[figure not shown]
$$M1 = 10$$

 $M2 = 10$
 $rho = 0.1000$

Estimated numbers of clusters and sample sizes:

$$K1 = 13$$

 $K2 = 13$
 $N1 = minimum 130$

N2 = minimum 130

Addendum 10/3/2022

Since we started recruitment on June 6th, 2022, we have completed 17 clusters (N total of 265 subjects), averaging 15 subjects per week. To preserve power in a cluster design trial, our statistician recommended completing the original plan of 26 clusters (13 clusters per group). Therefore, we anticipate that 405 patients will be enrolled in total. In addition, the trial will be considered completed whenever the final cluster number is reached. If we need more than 405 subjects to be enrolled, the trial will be paused, and an addendum will be submitted to the IRB.

References

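### The primary outcome is time to vaginal delivery, but the plan has no rule for how women delivered by cesarean enter the intention-to-treat primary analysis

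*Combined protocol and SAP*

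**What the plan says.** The primary outcome is worded in four places in the protocol.

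- Section 4.8 gives it as "Time to vaginal delivery measured from time of initial foley balloon placement to delivery".
- The hypothesis in Section 1 is that "Foley balloon under tension for cervical ripening results in shorter time to vaginal delivery compared to Foley balloon placed without tension".
- The purpose statement, also in Section 1, names no mode of delivery: "The purpose of our study is to examine time to delivery in nulliparous women undergoing induction of labor".
- The sample-size text in Section 12 names none either: "The primary outcome is time in minutes from Foley balloon placement to delivery".

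Section 4.2 and Section 12 both commit to intention-to-treat. For primary and secondary outcomes alike, Section 12 promises multilevel regression that allows for confounders and for correlation within weekly clusters. It mentions no time-to-event model, censoring or competing event. The trial is sized by a z test on two means. The control-arm input is given as "the primary outcome in control arm would be 1053.4 ± 535.73 mins", and the result is that "we will need 13 clusters (10/cluster) with complete ascertainment".

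Cesarean appears in Section 4.9 only as a secondary outcome (its incidence). Section 4.6 on withdrawals does not mention it.

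**The concern.** Some women in a trial of first-birth inductions will be delivered by cesarean, and the plan expects this. For the outcome as Section 4.8 words it, those women have no value. The plan nevertheless promises to analyse everyone as assigned, and its sizing treats every woman as contributing minutes.

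The two simplest ways to run a regression of minutes each break something in the plan. Leaving out women with cesareans selects on an event that happens after assignment and that tension may influence, so the remaining arms are no longer the randomised ones. Entering the time of cesarean changes the outcome from vaginal delivery to any delivery and scores an early cesarean as a good result.

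At stake is the meaning of the headline comparison: which women it covers and what quantity it estimates. If the rule is chosen after outcomes have been seen by arm, the result is also open to the charge that the rule was picked to suit it.

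**Working it through.** **1. The plan's own figure.** Inputs from Section 12: means 1053.40 and 1316.74 min (difference 263.34), SD 535.73, two-sided alpha 0.05, power 80%, 10 women per week, rho 0.1.

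- Per arm without clustering: 2 × (535.73 × 2.8016 / 263.34)² = 64.97.
- Design effect: 1 + (10 − 1) × 0.1 = 1.9, so 64.97 × 1.9 = 123.4 women, or 12.34 weeks, rounded up to 13.
- Result: 13 clusters and 130 women per arm, 260 in all. The stated figure reproduces. It assumes that every woman contributes a time.

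**2. Women without the Section 4.8 outcome.** The documents give no cesarean rate, so 10, 20 and 30% are assumptions. The planned total is 405.

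| Assumed cesarean rate | No time to vaginal delivery | Remaining |
|---|---|---|
| 10% | 40.5 | 364.5 |
| 20% | 81 | 324 |
| 30% | 121.5 | 283.5 |

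The remainder falls below the 260 sized only above 1 − 260/405 = 35.8%.

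**3. Do the two wordings estimate the same thing?** Suppose the plan's two means are observed means among vaginal births, and the cesarean share p is equal in both arms. The difference in mean time to any delivery is then (1 − p) × 263.34 + p × D, where D is the difference in mean cesarean time (no tension minus tension). The values of D are assumed.

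| D (min) | p = 10% | p = 20% | p = 30% |
|---|---|---|---|
| 0 | 237.0 | 210.7 | 184.3 |
| 263.34 | 263.3 | 263.3 | 263.3 |
| 400 | 277.0 | 290.7 | 304.3 |

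The two quantities can agree, or differ in either direction. This shows that they are different quantities; it does not measure bias.

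**4. Power.** With 26 weeks of 405/26 = 15.58 women and rho 0.1, a means test on all 405 has 88.4% power. On vaginal births alone, with the same SD and difference, it has 87.1, 85.5 or 83.5% at 10, 20 or 30% cesarean.

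A rough figure for a cause-specific hazard model needs strong assumptions:

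- proportional hazards and Weibull times;
- the plan's mean, SD and 25% ratio describe time to vaginal delivery in the absence of cesarean;
- the usual design effect carries over to hazards.

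The coefficient of variation 535.73/1053.40 = 0.509 gives shape 2.06, so the hazard ratio is 1.25^−2.06 = 0.631 (log −0.460). Power is Φ(√(events / design effect / 4) × 0.460 − 1.96). The design effect is 2.458 if all women in a week are counted, or 2.302, 2.146 and 1.990 if only vaginal births are counted. Power is then 80.0 to 82.5%, 75.2 to 80.7% or 69.5 to 78.4% at 10, 20 or 30% cesarean. With rho 0 it is 97% or more. These figures show only that the stated 80% does not transfer automatically.

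**5. Dates.** Recruitment began on 6 June 2022, and 17 weekly clusters were complete at the addendum of 3 October 2022. At that pace, 26 weeks end on 5 December 2022, before this version (28 February 2023). The documents do not confirm that date.

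**The case against.** Several points on the other side have force.

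- **The wording gap may be shorthand.** Section 4.8 and the hypothesis agree, and Section 4.8 itself ends on the bare word delivery. A reader might infer two competing primary outcomes, or a switch of outcome. The text does not support that. What stands is the missing cesarean rule, which is needed even if Section 4.8 governs everywhere.
- **The plan does not commit to a flawed analysis.** A means-test sizing does not fix the model, and multilevel regression could include a frailty model. Worst-rank scoring or censored regression would also keep these women. So it would be wrong to say that the sponsor must either drop them or use their cesarean times. But any of these rules has to be written down, and none is.
- **Other passages can be over-read.** Section 4.4 says that "The PI and faculty sponsor will review and validate the diagnosis for all subjects identified to have the primary outcomes", which might suggest that women without the outcome are set aside. It reads more naturally as general adjudication wording. Complete ascertainment may likewise mean only that no delivery record is missing.
- **A cause-specific model is not a complete cure.** Women leave the risk set at cesarean, so if slow labor leads to cesarean more often in one arm, the hazard ratio alone can mislead. This is correct, and it shapes the fix.
- **The documents are incomplete.** The flow diagram is not shown and the data collection sheet is not included. Either might contain a rule.

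**Conclusion.** The point holds: in the available text, the sole primary outcome has no rule for an expected group of women, and the two simplest regressions of minutes conflict either with intention-to-treat or with Section 4.8. This needs to be settled before the primary analysis. The reason is that the quantity to be estimated is undefined; no calculated distortion is involved.

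Two stronger conclusions are tempting. One is that the result will be biased toward one arm. The documents give no cesarean rates or times, so neither size nor direction can be stated. The other is that dropping cesareans leaves the trial underpowered. At 405 women, and if SD and difference are unchanged, the means test stays above 80% at the assumed 10 to 30% rates, so that is not supported.

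The number of women affected (about 41 to 122 of 405) rests entirely on the assumed rates.

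**What to change.** 1. Word the primary outcome identically in Sections 1, 4.8 and 12. If any delivery is meant, Section 4.8 and the hypothesis must say so.
2. If vaginal delivery is meant, keep every included woman in her assigned week's arm. Use a time-to-event analysis with cesarean as a competing event and clustering by week, for example a cause-specific hazard model with a random term for week. That stays within the multilevel regression already promised.
3. Read the hazard ratio together with cumulative incidence curves of vaginal delivery and of cesarean by arm, and report time to any delivery as supporting. Worst-rank scoring of cesareans, with allowance for week, is an acceptable alternative.
4. State whether 1053.4 ± 535.73 min includes cesarean births.
5. Confirm that the time of cesarean is abstracted; Section 4.9 lists only its incidence.
6. Reconcile Section 4.6 with intention-to-treat. It stops data collection for women who later meet an exclusion criterion. Malpresentation is one such criterion (Section 6), yet malpresentation after balloon removal is a secondary outcome in Section 4.9.
7. Date the change before outcomes are compared by arm, or disclose it as post hoc. Assignment is posted openly on the unit and enrolment may already be complete.

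The cost is mainly text, and no new data if the time of cesarean is already abstracted from the chart. The effect will no longer be a simple difference in mean minutes. The sample-size text should say that its 80% power rests on a means test, does not carry over directly, and may be somewhat lower at rho 0.1.

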4.9 Secondary Outcomes

- Request for IV/PO pain medications or epidural placement following placement of Foley balloon transcervical dilator during cervical ripening period
- Time of artificial rupture of membranes
- Incidence of malpresentation following removal of foley balloon
- Incidence of primary cesarean delivery
- Incidence of postpartum hemorrhage
- Chorioamnionitis (also known as "IAI," or "triple I"):
 - O A **presumptive diagnosis** of IAI (suspected triple I) can be made in women with:
 - Fever –≥39.0°C [102.2°F] or 38.0°C [100.4°F] to 38.9°C [102.02°F] on two occasions 30 minutes apart, without another clear source PLUS one or more of the following:
 - Baseline fetal heart rate >160 beats/min for ≥10 minutes, excluding accelerations, decelerations, and periods of marked variability
 - Maternal white cell count >15,000/mm3 in the absence of corticosteroids and ideally showing a left shift (bandemia)
 - Purulent-appearing fluid coming from the cervical os visualized by speculum examination
 - O A **confirmed diagnosis** of IAI can be made in women with:
 - All of the above PLUS one or more of the following objective laboratory findings:
 - Positive Gram stain of amniotic fluid
 - Low glucose level in amniotic fluid
 - Positive amniotic fluid culture
 - High white cell (WBC) count in amniotic fluid in the absence of a bloody tap
 - Histopathologic evidence of infection or inflammation or both in the placenta, fetal membranes, or the umbilical cord vessels (funisitis)
- Endometritis must meet the following criteria:
 - O Infection occurs within 30 days after the operative procedure AND
 - o Infection presumed to involve the uterus AND
 - O Patient has at least one of the following:
 - Purulent drainage from a drain that is placed through a stab wound into the abdomen or pelvis
 - Organisms isolated from an aseptically-obtained culture of fluid or tissue in the organ / space
 - An abscess or other evidence of infection involving the abdomen or pelvis that is found on direct examination, during re-operation, or by histopathologic or radiologic examination
- Neonatal infection, defined as sepsis, fever, positive cultures, or a suspicious clinical course that warranted treatment with antibiotics

- APGAR scores
- NICU admission rates
- Neonatal hospital length of stay

5. Criteria for Inclusion of Subjects:

- Women >18 and <50
- Term induction of labor
- Nulliparous
- Vertex
- Singleton
- Plan for Foley balloon placement by the managing obstetrics team
- Cervical exam less than 3 cm dilated and less than or equal to 60% effaced

6. Criteria for Exclusion of Subjects:

- Patient unwilling or unable to provide verbal consent
- Fetal demise or major congenital anomaly
- Preterm (<37 0/7weeks)
- Multiple gestation
- Previous uterine surgery
- Abnormal placentation
- Malpresentation
- Magnesium infusion for preeclampsia with severe features
- Prelabor rupture of membranes
- Fetal growth restriction
- Non-reassuring fetal heart rate tracing prior to inclusion

7. Sources of Research Material: Electronic medical chart / records

8. Potential Risks:

No significant adverse effects are expected with the use of transcervical Foley balloons for mechanical dilation. Foley balloons are the standard of care for induction of labor at UTMB. The most significant risks are vaginal bleeding due to cervical trauma and incidental rupture of membranes, as well as pain or discomfort with placement. The patient will undergo inpatient induction of labor, so any adverse reaction would be promptly detected and addressed.

8.1. Randomization risk

There are no foreseen randomization risks as both the study and control group are currently methods utilized for induction of labor at UTMB.

8.2. Loss of Confidentiality

Any time information is collected, there is a potential risk for loss of confidentiality. Every effort will be made to keep patient's information confidential; however, this cannot be guaranteed.

8.3 Mechanical dilator (Foley balloon):

1. No tension has no adverse effects except possibly a longer cervical ripening time. A foley balloon placed without tension is currently used as an accepted form of induction of labor at UTMB and is not thought to have any increased risks. Foley balloons placed with and without

tension are both considered standard of care at our institution, with one not thought to have any more risk.

9. Subject Safety and Data Monitoring

The PI and research collaborators will be responsible for monitoring the safety of this study. The report will include participant demographics, expected versus actual recruitment rates, summary of any quality assurance or regulatory issues, summary of adverse events (AE's) or serious adverse events (SAE's) which may have occurred, and any changes in the protocol because of these issues.

The PI's and collaborators will ensure all aspects of data quality, including monitoring for adherence to consent procedures, inclusion and exclusion criteria, valid abstraction, correct entry, timeliness, and responsiveness to data queries. The team will be meeting every quarter to review procedures and resolve any issues that need to be addressed.

A final report will be submitted yearly with every continuation review IRB application.

Data will be collected and stored with the participant ID code only. The master enrollment log linking patient identifiers with study ID numbers will be kept in a password-protected database on the OB/GYN department's internal server separate from the data. Data collection forms will be used. Data on these forms devoid of personal identifiers will be securely stored at our perinatal research division. The principal investigator or approved research staff will be available to monitor the data and correct any discrepancies based on source documents if needed.

10. Procedures to Maintain Confidentiality

- The data collected will be indirectly linked to the subject by patient's MRN number.
- When the subject accepts to participate in the study, a number will be attributed to the patient, and this number will be entered on the data collection sheet.
- The data collected will be transferred to the PI's password-secured UTMB computer that is stored in a locked room using an USB flash drive.
- The study PI will be the only person to have a list with the number designated to each subject and the corresponding patient's MRN number. This list will be kept in a locked cabinet of the PI's locked UTMB office. This identifier is needed to access and analyze demographic data. During analysis of the data, all identifiers will be deleted.
- Data will not be disclosed to outside persons or entities.

11. Potential Benefits

Subjects who undergo Foley balloon placement with tension may be at decreased risk for protracted labor. If this is the case, our study stands to benefit women who have a Foley balloon or other mechanical dilator placed in future cases of labor induction.

12. Statistical Approach

Analysis will be performed by intention-to-treat. Univariable and multivariable analysis will be used to describe the population in the study and to identify potential confounding variables. For this analysis, normality will be tested using Shapiro-Wilk method. Demographics and descriptive statistics will be used to provide a profile of the study sample. Data will be either shown as median +/- IQR or mean +/- SDEV. Bivariate tests such as t test, Pearson's chi square, and Mann-Whitney tests will be used as indicated to identify any key differences in the profiles of subjects across study conditions. Statistical

analyses of primary and secondary outcomes between study groups will be performed by multilevel regression analysis accounting for both confounding variables as well as adjusting for any potential intra class correlation that may arise from the cluster study design.

Sample size was calculated based on the determination of superiority. The primary outcome is time in minutes from Foley balloon placement to delivery. For the sample size calculation, based on our prior published data¹⁰, the primary outcome in control arm would be 1053.4 ± 535.73 mins. Using difference rate of 25% (No tension group: 1316.748 mins), power of 80% and 2-sided alpha of 0.05, and the assumption that 10 eligible subjects are induced per week, we previously estimate that we will need 13 clusters (10/cluster) with complete ascertainment. Currently, we have recruited approximately 15 subjects per cluster. For the previously planned 13 clusters in each group (26 clusters total), we estimate a final total number of 405 subjects. Final sample size: 405 (minimum of 130/group). This difference between both methods is clinically significant. Detailed: Estimated sample sizes for a two-sample means test (z test); Study parameters: alpha Since this is a single center study in one same location the intra-cluster correlation coefficient of variance (rho) should be close to 0 and would give us a sample size of 140, but we chose the worst-case scenario of a rho of 0.1 (graph).

This trial will be registered with Clinical Trials Register (Clinicaltrials.gov), before recruitment is initiated and after IRB approval.

SAMPLE SIZE COMPUTATION power twomeans 1053.399 1316.74, sd(535.73) m1(10) m2(10) rho(0.1)

Performing iteration ...

Estimated numbers of clusters for a two-sample means test Cluster randomized design, z test assuming sd1 = sd2 = sd Ho: m2 = m1 versus Ha: m2 != m1

Study parameters:

Cluster design:

[figure not shown]
$$M1 = 10$$

 $M2 = 10$
 $rho = 0.1000$

Estimated numbers of clusters and sample sizes:

$$K1 = 13$$

 $K2 = 13$
 $N1 = minimum 130$

N2 = minimum 130

Addendum 10/3/2022

Since we started recruitment on June 6th, 2022, we have completed 17 clusters (N total of 265 subjects), averaging 15 subjects per week. To preserve power in a cluster design trial, our statistician recommended completing the original plan of 26 clusters (13 clusters per group). Therefore, we anticipate that 405 patients will be enrolled in total. In addition, the trial will be considered completed whenever the final cluster number is reached. If we need more than 405 subjects to be enrolled, the trial will be paused, and an addendum will be submitted to the IRB.

References

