4.2. Operationalization

Randomization

This study will use cluster randomization, with each week group described as a cluster. Prior studies have investigated induction of labor methods utilizing cluster randomization. Cluster randomization will be computer generated and will assign each cluster (weeks) to the control or study group. Both the study group and the control group are considered part of the standard of care for induction of labor at UTMB. Clusters will be block randomized in groups (weekly).

Labor and Delivery Unit/Staff

Several training sessions will occur to notify all staff of the trial and the protocol. Training sessions will include a copy of the protocol to review as well as follow-up email communication. The PI will also be available for questions. All operations will be also reviewed with all staff.

At shift change 0630-0700 am and pm every Monday to Friday, randomization assignments will be announced to all nurses and providers on the Labor and Delivery unit. All staff caring for subjects during the week of randomization will be notified of the cluster randomized for that week for all labor inductions. Notifications and plastic tags will be placed in the workstations for the providers and at all nursing stations on labor and delivery and at the patient's room door stating Tension or No Tension. A notification will also be placed at the work station of the study team. All study team in the Perinatal Research Department will also be notified via email at the beginning of each week.

An Epic order will be placed by provider specifying "Foley balloon under tension" or "Foley balloon No Tension" according to the randomization assignment.

Subjects under treatment conditions before this time will be included as part of the treatment block assignment at the time of inclusion and will not be allowed to cross over. The subject will be included in the analysis by intention-to-treat once the randomization assignment has been made.

The cluster randomized trial design is such that each week, the chosen method of induction of labor in subjects meeting inclusion criteria is randomized to either the Tension standard of care (control group) or No Tension standard of care (study group). All subjects who would meet inclusion criteria for foley balloon induction of labor will be participants in the study. The two methods of induction being compared are currently accepted and practiced standards used for women with an unfavorable cervix who

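### Section 12 compares baseline profiles with tests that treat women as independent although weeks are randomised, so their p-values are too small for any positive week-level correlation (low severity)

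*Combined protocol and SAP*

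**What the plan says.** Section 4.2 fixes the unit of randomisation: "This study will use cluster randomization, with each week group described as a cluster". The sample size text in Section 12 and its October 2022 addendum plan 13 weeks per arm, 26 in total. They project 405 women, at roughly 15 per week instead of the 10 first assumed.

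The analysis paragraph of Section 12 makes three statements that bear on this point:

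- On the purpose of the descriptive work: "Univariable and multivariable analysis will be used to describe the population in the study and to identify potential confounding variables".
- On comparing subject profiles between the arms: "Bivariate tests such as t test, Pearson's chi square, and Mann-Whitney tests will be used as indicated to identify any key differences". No allowance for the week is mentioned, and no significance level is given for these tests.
- On the primary and secondary outcomes: a multilevel regression that accounts for confounders and is also "adjusting for any potential intra class correlation that may arise from the cluster study design". This sentence covers outcomes only.

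On the size of the correlation, the sample size text expects rho to be close to zero because there is a single centre, "but we chose the worst-case scenario of a rho of 0.1". That figure is an input for time to delivery. No ICC is given for any baseline variable.

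**The concern.** The plan recognises clustering in its sample size and in its outcome models, but not in the baseline comparison. In their standard form the t test, Pearson chi-square and Mann-Whitney test take their standard errors from about 405 independent women. If women induced in the same week are alike on some characteristic, those standard errors are too small, and ordinary week-to-week variation is flagged as a difference between arms more often than the nominal level implies.

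Two features of this trial give the baseline comparison more weight than usual. First, Section 4.2 has the week's assignment announced to staff and posted on the unit, and under Section 5 a woman qualifies only if her team plans a Foley balloon. The arm is therefore known before entry, and a reader will look at the baseline table for signs that this knowledge influenced who entered. Second, the same paragraph of Section 12 uses its descriptive analyses to look for confounders. It lists no covariates for the outcome models, so a spurious flag could influence which covariates enter them.

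**Working it through.** **Inputs.** From Section 12: control mean and SD ("the primary outcome in control arm would be 1053.4 ± 535.73 mins"); comparison mean 1316.74 min in the sample size command; "power of 80% and 2-sided alpha of 0.05"; 10 women per week as first planned; 26 weeks and 405 women as now projected; rho 0.1 as worst case. Assumed here: a two-sided 5% level for the baseline tests, and a range of ICCs for baseline variables.

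**Step 1: reproduce the plan's figure.** The difference is 1316.74 − 1053.399 = 263.341 min. Under independence, n per arm = 2 × [535.73 × (1.960 + 0.842) / 263.341]² = 64.97. With 10 women per week and rho 0.1 the design effect is 1 + 9 × 0.1 = 1.9. This gives 64.97 × 1.9 = 123.4 women, or 12.34 weeks, rounded up to 13 weeks and 130 women per arm. At rho 0, 64.97 / 10 = 6.5, rounded up to 7 weeks per arm and 140 women in total. Both of the plan's figures reproduce.

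**Step 2: women per week.** 405 / 26 = 15.58. The addendum's running count agrees: 265 / 17 = 15.59.

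**Step 3: true size of a nominal 5% test that ignores weeks.** Design effect DE = 1 + (15.58 − 1) × rho. True size = 2 × [1 − Φ(1.96 / √DE)].

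| ICC of the baseline variable | DE | True size | Multiple of 5% |
|---|---|---|---|
| 0 | 1.00 | 5.0% | 1.0 |
| 0.01 | 1.146 | 6.7% | 1.3 |
| 0.02 | 1.292 | 8.5% | 1.7 |
| 0.05 | 1.729 | 13.6% | 2.7 |
| 0.1 | 2.458 | 21.1% | 4.2 |

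At 10 women per week and ICC 0.1, DE is 1.9 and the size 15.5% (3.1 times nominal). The larger weeks make the inflation somewhat worse.

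**Step 4: simulation check.** The set-up was 26 weeks of 15 or 16 women (405 in total), independent week effects and no true difference. There were 10,000 runs per setting (5,000 for Mann-Whitney). The chi-square test used an assumed prevalence of 30%.

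| ICC | t test | Mann-Whitney | Chi-square | t test on week means |
|---|---|---|---|---|
| 0 | 5.0% | 4.6% | 5.2% | 4.8% |
| 0.01 | 6.8% | 6.0% | 6.5% | 4.7% |
| 0.05 | 13.1% | 12.5% | 13.6% | 4.6% |
| 0.1 | 20.4% | 20.3% | 21.9% | 5.2% |

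The formula holds for all three named tests, and a test on week means stays close to 5% throughout.

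**Step 5: chance spread of a standardised difference.** With 202.5 women per arm the standard error under independence is √(2 / 202.5) = 0.10. At ICC 0.1 it is 0.10 × √2.458 = 0.16. Standardised differences are thus also more variable than individual-level reasoning suggests.

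**The case against.** **The ICC.** The strongest objection is that the large figure borrows an ICC. Rho 0.1 is a deliberately pessimistic planning value for time to delivery, the same sentence expects a value near zero, and nothing is said about maternal characteristics. A reader might infer that the baseline tests run at four times their nominal error rate at the plan's own ICC. The documents do not support that, because the plan states no ICC for these variables. At 0.01 to 0.02 the inflation is only 1.3 to 1.7 times. This objection stands and sets the severity.

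**Blocking.** Section 4.2 says that weeks are randomised in blocks. If part of the similarity within weeks reflects slow calendar change, blocking over time balances some of it between arms, and the true rate falls below the formula, which assumes independent week effects. The block size is not given, so the reduction cannot be calculated. This stands as a further reason to treat the figures as upper bounds at each ICC.

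**The outcome results.** A reader might also infer that the trial's main tests are anti-conservative for the same reason. The text says otherwise: the outcome models are multilevel and adjust for intra-class correlation. The only route from the baseline tests to the results is covariate choice, and Section 12 attaches no explicit selection rule to these tests.

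**The role of the tests.** Nor does the plan call them a check for selection bias or set a decision threshold. That use is a reader's likely interpretation, not a planned step.

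**Wording.** The list of tests is illustrative and to be applied where indicated, which leaves some latitude. But every test named ignores the week, and nothing extends the cluster adjustment to profiles.

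**Conclusion.** The point holds at low severity. As written, Section 12 tests baseline profiles as if about 405 women had been individually randomised, when 26 weeks were. For any positive week-level ICC the p-values are too small under the independent-week model used here. The true size of a nominal 5% test runs from about 6.7% at ICC 0.01 to 21% at 0.1. The upper end applies only if a baseline variable is as strongly correlated within weeks as the plan's worst case for the outcome. If baseline ICCs are near zero, the inflation is small.

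These figures assume a 5% level for the baseline tests, about 15.6 women per week of nearly equal size, and no gain from blocking. The consequence is confined to how comparable the arms appear and, possibly, to which covariates are adjusted for. It does not overturn the planned primary or secondary outcome tests.

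**What to change.** Replace the sentence in Section 12 so that any between-arm comparison of baseline variables respects the week. Either of these repairs the defect directly:

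- a mixed model with a random effect for week and a small-sample correction, since there are only 13 weeks per arm; or
- a test on week-level means or proportions.

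An acceptable alternative is to describe baseline variables by arm with standardised differences and no significance tests. This is partly a reporting preference. It should carry no rigid cut-off, because clustering widens the chance spread of these differences too.

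Listing the adjustment covariates for the outcome models in advance would close the route from baseline tests to covariate choice.

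The cost is slightly more analysis work and less power to flag baseline differences, so a modest true imbalance is less likely to reach significance. Dropping the tests altogether also gives up a formal check in a trial where the arm is known before entry. No new data and no change to enrolment or care are needed.
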